## Amendment 1, 04 December 2019

### Main Rationale for the Amendment:

The purpose of this amendment was to add the IST review of safety data through 7 days after the first vaccination at the **CCI** dose level and to include localized axillary swelling or tenderness ipsilateral to the vaccination arm as a solicited local adverse reaction (AR).

The summary of changes table provided here describes the major changes made in Amendment 1 relative to the original protocol, including the sections modified and the corresponding rationales. The synopsis of Amendment 1 has been modified to correspond to changes in the body of the protocol. Minor editorial and grammatical corrections were also made.

### Summary of Major Changes from the Original Protocol to Protocol Amendment 1:

Section # and Name	Description of Change	Brief Rationale
Title page, Protocol Approval page, page headers	Updated the protocol version and date	To reflect the new version and date of the protocol.
Section 1.2 Schema	Added IST review for mRNA-1647 CCI groups	To add the IST review of safety data through 7 days after the first vaccination at the mRNA-1647 CCI dose level.
Section 1.3 Schedule of Assessments	Added header row for Days Since Most Recent Vaccination to Table 1  Updated the header row for Study Visit Day and updated footnotes to include review of ARs and add blood collection for cell-mediated immunity for Table 1	To add “Days Since Most Recent Vaccination” to the table.  To add blood collection for cell-mediated immunity.
Section 3.2.3 Exploratory Endpoints	Removed endpoints for plasmablasts and circulating T, B, and NK cells	To remove the exploratory endpoints of total and/or antigen-specific plasmablasts and circulating T, B, and NK cells.
Section 4.2 Scientific Rationale for Study Design	Added IST review through 7 days after the first vaccination	To add the IST review of safety data through 7 days after the first vaccination at the CCI dose level.
Section 5.2 Inclusion Criteria	Added text for male participants with partners who become pregnant before screening in inclusion criterion #7	To add that male participants with partners who have become pregnant prior to the participant’s screening visit are eligible to participate in the study.

Section # and Name	Description of Change	Brief Rationale
Section 6.1 Description of Study Vaccine	Updated storage temperature	To correct and clarify investigational product storage temperature ranges (°C and °F).
Section 6.2.4 Clinical Trial Material Storage	Added storage temperature	To correct and clarify investigational product storage temperature ranges (°C and °F).
Section 8.3 Collect Demographic and Baseline Data	Added age and replaced date of birth with month and year of birth	To correct parameters collected for baseline and demographic data.
Section 8.8 Sampling for Safety and Immunogenicity Assessments	Updated timing of laboratory assessment sample collection, added text for collection of blood for cell-mediated immunity, updated blood volumes for chemistry and coagulation (Table 1)	To reduce the scope of cell-mediated immunogenicity testing from testing all participants to testing a subset of participants and to correct study days listed for sample collection.
Section 8.8.2 Blood Sampling for Safety Laboratory Testing	Updated timing of laboratory assessment sample collection	To correct study days listed for sample collection.
Section 8.8.4 Blood Sampling for Cell-mediated Immunogenicity	
Added text for collection of blood for cell-mediated immunity
 
Removed IgG-memory B-cell responses, Pentamer-specific IgG memory B-cell responses, and gB-specific CD4 and CD8 T-cells secreting interleukin (IL)-2 and/or tumor necrosis factor (TNF)-<math>\alpha</math> from the list of cell-mediated immunogenicity parameters
 
Clarified the cell-mediated immunogenicity parameters included gB-specific and Pentamer-specific CD4 and CD8 IFN-<math>\gamma</math>-secreting T-cells as measured by ELISpot
	To reduce the scope of cell-mediated immunogenicity testing and reflect changes to the exploratory endpoints.

Section # and Name	Description of Change	Brief Rationale
Section 8.9.1.3 Solicited Adverse Reaction	
Added text for localized axillary swelling or tenderness ipsilateral to the vaccination arm and updated Table 2 accordingly
 
Clarified guidance for follow-up of ARs within 7 days after study vaccination and ARs recorded in eDiaries beyond Day 7
 
Updated timing of review of completed eDiaries
	
To include localized axillary swelling or tenderness ipsilateral to the vaccination arm as a solicited local AR. To clarify that ARs recorded in eDiaries beyond Day 7 should be reviewed either via phone call or at the following study visit. To update guidance for ARs within 7 days after study vaccination. To adjust days when review of completed eDiaries takes place.

Section 8.9.2 Recording of Adverse Events, Serious Adverse Events, and Medically-Attended Adverse Events	
Clarified guidance for follow-up of ARs within 7 days after study vaccination
 
Added text to clarify when the study site staff will contact the participant and added text on reporting pregnancies
	
To clarify that the study site staff will contact the participant within 24 hours of becoming aware of any reports of Grade 3 ARs, presence of any rash, or presence of any underarm swelling or tenderness. To add the description of pregnancy reporting procedures.

Section 8.9.5 Assessment of Causality	
Added that all solicited ARs will be considered causally related
	
To clarify that all solicited ARs (local and systemic) will be considered causally related to vaccination.

Section 8.9.8 Pause Rules	
Updated Table 4 footnote to include text on IST requested ad hoc SMC meetings
	
To correct the description of the ad hoc SMC review of Pause Rules.

Section 9.7 Interim Analyses and Data Monitoring Committee Analyses	
Updated timings for safety and immunogenicity data collection
	
To reduce the scope of cell-mediated immunogenicity testing from testing all participants to testing a subset of participants and to correct study days listed.

Section 9.7.1 Study Safety Oversight	
Added text about IST review
	
To add the IST review of safety data through 7 days after the first vaccination at the CC1 dose level.

Section 10.5 Informed Consent Process	
Added text for future testing of samples
	
To clarify process for future testing and communication of results of future testing.

Section 10.9 Study Safety Oversight by Internal Safety Team and Safety Monitoring Committee	
Added text for IST review
	
To add the IST review of safety data through 7 days after the first vaccination at the CC1 dose level.

Section # and Name	Description of Change	Brief Rationale
Appendix 2 Schedule of Events for Participants Completing the First 2 Vaccinations Only	Added header row for Days Since Most Recent Vaccination, updated the header row for Study Visit Day, and updated footnotes to include review of ARs and add blood collection for cell-mediated immunity for Table 6 and Table 7	To add “Days Since Most Recent Vaccination” to the tables.
Appendix 3 Toxicity Grading Scale Tables	Updated solicited AR grading	To clarify grading of solicited ARs is assessed based on the modified 2007 CBER toxicity grading scale.

ANCOVA	analysis of covariance
Solicited AR	solicited adverse reaction
AST	alkaline phosphatase
BMI	body mass index
CBL	Moderna Clinical Biomarker Lab
CI	confidence interval
CMI	cell-mediated immunogenicity
CMV	cytomegalovirus
COVID	Coronavirus
CRO	contract research organization
CSP	clinical study protocol
CSR	clinical study report
DHHS	Department of Health and Human Services
eCRF	electronic case report form
eDiary	electronic diary
ELISA	enzyme-linked immunosorbent assay
ELISpot	enzyme-linked immunospot
FACS	fluorescence-activated cell sorting
FAS	full analysis set
FSH	follicle-stimulating hormone
gB	glycoprotein B
GLSM	geometric least squares means
GMR	geometric mean ratio
GMT	geometric mean titer
HBsAg	hepatitis B virus surface antigen
HIV	human immunodeficiency virus
ICS	intracellular cytokine staining
IFN	interferon
IgG	immunoglobulin G
IRT	interactive response technology
LLOQ	lower limit of quantification
MAAEs	medically-attended adverse events
MedDRA	Medical Dictionary for Regulatory Activities
MMRM	mixed-effect model for repeated measures
mRNA	messenger ribonucleic acid
nAb	neutralizing antibody
PBMC	peripheral blood mononuclear cell
Pentamer	pentameric gH/gL/UL128/UL130/UL131A glycoprotein complex
PP	per-protocol
PT	preferred term

Abbreviation	Definition
PT	prothrombin time
PTT	partial thromboplastin time
REML	restricted maximum likelihood
SAE	serious adverse event
SAP	statistical analysis plan
SAS	Statistical Analysis System
SD	standard deviation
SMQ	Standardized MedDRA Query
SOC	system organ class
TEAE	treatment-emergent adverse event
ULOQ	upper limit of quantification
WHO	World Health Organization
WHODD	World Health Organization drug dictionary

1. Introduction

This statistical analysis plan (SAP), which describes the planned analyses for Study mRNA-1647-P202, is based on the most recent approved clinical study protocol (CSP), Version Amendment 5, dated 27 May 2021 and the most recent approved electronic case report form (eCRF) Version 14.002, dated 02 Dec 2022.

This SAP version 5.0 is to update the planned analyses before the final database lock and full unblinding, after which the final analysis will be performed.

In addition to the information presented in the statistical analysis plan section of the protocol (Section 9) which provides the principal features of analyses for this study, this SAP provides statistical analysis details/data derivations. It also documents modifications or additions to the analysis plan that are not “principal” in nature and result from information that was not available at the time of protocol finalization.

Study mRNA-1647-P202 is a Phase 2, randomized, observer-blind, placebo-controlled, dose-finding study to evaluate the safety and immunogenicity of messenger ribonucleic acid (mRNA)-1647 in healthy adults who are either cytomegalovirus (CMV)-seronegative or CMV-seropositive at enrollment.

PPD Biostatistics and programming team, designee of Moderna Biostatistics and Programming department, will perform the statistical analysis of the safety, reactogenicity, and immunogenicity data; Statistical Analysis System (SAS) Version 9.4 or higher will be used to generate all statistical outputs (tables, figures, listings, and datasets). The SAP will be finalized and approved prior to the first interim analysis data extraction and treatment unblinding for the study. If the methods in this SAP differ from the methods described in the protocol, the SAP will prevail.

In this document, subject and participant are used interchangeably; vaccination, injection, and dose are used interchangeably; vaccination group and treatment group are used interchangeably.

2. Study Objectives

2.1. Primary Objective

The primary objectives of the study are as follows:

- To evaluate the safety of different dose levels of mRNA-1647 vaccine administered in a 3-vaccination (0, 2, 6-month) schedule.

- To evaluate neutralizing anti-CMV antibody responses against fibroblast and epithelial cell infection following vaccination with mRNA-1647 at different dose levels administered in a 3-vaccination (0, 2, 6-month) schedule.

2.2. Secondary Objectives

The secondary objectives of the study are as follows:

- To evaluate antigen-specific antibody responses following vaccination with mRNA-1647 at different dose levels in a 3-vaccination schedule.
- To evaluate the immunogenicity of mRNA-1647 by CMV serostatus at enrollment.

2.3. Exploratory Objectives

The exploratory objectives of the study are as follows:

- To evaluate cell-mediated immune responses following vaccination with mRNA-1647 at different dose levels.
- In CMV-seropositive participants, to assess possible effects of immunologic response following vaccination with mRNA-1647 compared to placebo.

3. Study Endpoints

3.1. Primary Endpoints

The primary endpoints of the study are as follows:

- Solicited local and systemic adverse reactions (ARs) through 7 days after each vaccination.
- Unsolicited adverse events (AEs) through 28 days after each vaccination.
- Medically-attended adverse events (MAAEs) through 6 months after the last vaccination, and serious adverse events (SAEs) throughout the entire study period.
- Geometric mean titer (GMT) of serum neutralizing anti-CMV antibodies against epithelial cell infection and against fibroblast infection, and associated geometric mean ratio (GMR) of post-baseline/baseline titers at each timepoint.
- Proportion of participants with ≥ 2 -fold, 3-fold, and 4-fold increases in neutralizing antibody (nAb) over baseline against epithelial cell infection and against fibroblast infection at each timepoint.

3.2. Secondary Endpoints

The second endpoints of the study are as follows:

- GMT of anti-glycoprotein B (gB) specific immunoglobulin G (IgG) and anti-pentameric gH/gL/UL128/UL130/UL131A glycoprotein complex (Pentamer) specific IgG as measured by enzyme-linked immunosorbent assay (ELISA), and associated GMR of post-baseline/baseline titers at each timepoint.
- GMT, GMR, and proportion of participants with ≥ 2 -fold, 3-fold, and 4-fold increases over baseline of serum nAb against epithelial cell infection and against fibroblast infection at each timepoint, and GMT and GMR of antigen-specific IgG (ELISA) at each timepoint, in the CMV-seropositive group and in the CMV-seronegative group.

3.3. Exploratory Endpoints

The exploratory endpoints of the study are as follows:

- gB- and Pentamer-specific interferon (IFN)- γ -secreting T-cell responses as measured by enzyme-linked immunospot (ELISpot) assay.*
- Exploratory assays to assess for anti-CMV immunologic response or for primary CMV infection may be performed at the discretion of the Sponsor.

* Reflects the description of this exploratory endpoint in the protocol; refer to Section 7 on the change of the assay for this endpoint from ELISpot to ICS.

[figure not shown]
4. Study Design

4.1. Overall Study Design

This is a Phase 2, randomized, placebo-controlled, observer-blind, dose-finding trial enrolling healthy participants 18-40 years of age.

A schematic of the study design is shown in [Figure 1](#).

Figure 1 Study Design Schematic

Abbreviations: IST= internal safety team; mRNA = messenger ribonucleic acid.

In protocol amendment version 3, Part 2 of the study was added to evaluate the safety and immunogenicity of the selected CCI mRNA-1647 dose level in a larger female population, which is the target population for Phase 3 development.

CMV-seronegative and CMV-seropositive groups will be enrolled at the same time. Randomization will be stratified by CMV serostatus (via an Interactive Response Technology [IRT]) in a sequential manner into the CCI dose levels in Part 1 and the CCI dose level in Part 2. At each dose level, participants will be randomized in 3:1 ratio to either mRNA-1647 vaccine or placebo, administered in a 3-vaccination (0, 2, 6-month) schedule.

Treatment Arms

Part 1 CMV-seronegative Group (males and females aged 18-40 years)

- Approximately 60 participants randomized 3:1 to receive either CCI of mRNA-1647 vaccine or placebo in a 0, 2, 6-month schedule
- Approximately 60 participants randomized 3:1 to receive either CCI of mRNA-1647 vaccine or placebo in a 0, 2, 6-month schedule

- Approximately 60 participants randomized 3:1 to receive either CCI of mRNA-1647 vaccine or placebo in a 0, 2, 6-month schedule

Part 1 CMV-seropositive Group (males and females aged 18-40 years)

- Approximately 24 participants randomized 3:1 to receive either CCI of mRNA-1647 vaccine or placebo in a 0, 2, 6-month schedule
- Approximately 24 participants randomized 3:1 to receive either CCI of mRNA-1647 vaccine or placebo in a 0, 2, 6-month schedule
- Approximately 24 participants randomized 3:1 to receive either CCI of mRNA-1647 vaccine or placebo in a 0, 2, 6-month schedule

Part 2 CMV-seronegative Group (females aged 18-40 years)

- Approximately 80 participants randomized 3:1 to receive either CCI of mRNA-1647 vaccine or placebo in a 0, 2, 6-month schedule

Part 2 CMV-seropositive Group (females aged 18-40 years)

- Approximately 120 participants randomized 3:1 to receive either CCI of mRNA-1647 vaccine or placebo in a 0, 2, 6-month schedule

4.2. Sample Size and Power

There is no hypothesis testing in this study. The number of proposed participants is considered sufficient to provide a descriptive summary of the safety and immunogenicity of different dose levels of mRNA-1647.

Approximately 252 participants will be enrolled in Part 1 of the study with approximately 189 participants randomized to mRNA-1647 vaccine. With 189 participants, there is > 95% probability to observe at least one participant with an AE if the true incident of the AE is 2%. Approximately 200 participants will be enrolled in Part 2 of the study with approximately 150 participants randomized to CCI of mRNA-1647. With 150 participants who are randomized to receive CCI of mRNA-1647, there is > 90% probability to observe at least one participant with an AE if the true incident of the AE is 2%.

4.3. Randomization

In Part 1, randomization will be stratified by CMV serostatus group (via IRT) in a sequential manner into one of 3 arms evaluating different dose levels of mRNA-1647 administered in a 3-vaccination (0, 2, 6-month) schedule. In Part 2, randomization will be stratified by CMV

serostatus group (via IRT) and participants will be randomized in 3:1 ratio to receive CCI of mRNA-1647 or placebo in a 3-vaccination (0, 2, 6-month) schedule.

4.4. Blinding and Unblinding

As the appearance of vaccine and placebo differs, this study will be conducted as an observer-blind study. Clinical site staff with the responsibility of safety assessments including the Investigators, participants, and Sponsor personnel (or its designees) are blinded to treatment assignment. Only designated unblinded personnel qualified to prepare and/or administer vaccine are aware of the treatment assignment.

Except in the case of medical necessity, a participant's treatment should not be unblinded while participating in the study without the approval of the Sponsor. The treatment code should be broken only if the Investigator/physician in charge of the participant feels that the case cannot be treated without knowing the identity of the study vaccine. Instructions regarding emergency unblinding will be provided to the Investigator and is discussed in Section 8.11 of the protocol.

The Sponsor will remain blinded to individual treatment assignment up until the 7-month interim analyses. At the 3-month and 7-month interim analyses, only pre-identified Sponsor and unblinded Contract Research Organization (CRO) team members as specified in the study Data Blinding Plan will be unblinded to review treatment level results and individual listings. Participants, Investigators, and study sites will remain blinded to individual treatment assignments until the end of the study procedures.

Upon completion of final study procedures, including the final assessment and recording of MAAEs and SAEs, the participant's treatment assignment may be unblinded, using the IRT system, to the Investigator, participant, Sponsor, and Sponsor representatives/delegates. The primary purpose for unblinding the participant's treatment assignment upon completion of the final procedures is to allow the Investigator to assess the eligibility of seropositive participants for enrollment into the extension study (mRNA-1647-P202-EXT). However, the treatment assignment may also be unblinded upon completion of final study procedures for seronegative participants and participants who do not wish to enroll in Study mRNA-1647-P202-EXT. The Investigator is responsible for documenting the treatment unblinding for each participant.

5. Analysis Populations

The following analysis sets are defined: Randomized Set, Solicited Safety Set, Safety set, Full Analysis set (FAS), and Per-Protocol (PP) set.

5.1. Randomized Set

The Randomized Set consists of all participants who are randomized in the study, regardless of the participant's treatment status in the study. This set will be used for descriptive purposes.

5.2. Solicited Safety Set

The Solicited Safety Set consists of all participants who are randomized and received any study vaccination, and contribute any solicited AR data, ie, have at least one post-baseline solicited safety (eDiary) assessment. The Solicited Safety Set will be used for the analyses of solicited ARs and participants will be included in the vaccination group corresponding to the study vaccination they actually received.

In addition, a subset of the Solicited Safety Set is defined for each vaccination. The First (Second; Third) Vaccination Solicited Safety Set consists of all subjects in the Solicited Safety Set who have received the first (second; third) study vaccination and have contributed any solicited AR data (eDiary) from the time of first (second; third) study vaccination through the following 6 days.

Subjects will be analyzed according to the vaccination group a subject received, rather than the vaccination group to which the subject is randomized. Subjects who receive a vaccination/injection that is different from the vaccination/injection which the subject is randomized to will be summarized under the highest dose of vaccination group (i.e., mRNA-1647 **CCI** > mRNA-1647 **CCI** > mRNA-1647 **CCI** > Placebo).

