##### Part 1 CMV-seropositive Group (males and females aged 18-40 years)

- Approximately 24 participants randomized 3:1 to receive either **CCI** of mRNA-1647 vaccine or placebo in a 0, 2, 6-month schedule
- Approximately 24 participants randomized 3:1 to receive either **CCI** of mRNA-1647 vaccine or placebo in a 0, 2, 6-month schedule
- Approximately 24 participants randomized 3:1 to receive either **CCI** of mRNA-1647 vaccine or placebo in a 0, 2, 6-month schedule

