### **9.4.2. Solicited Safety Set**

The Solicited Safety Set consists of all participants who are randomized and received any study vaccination, and contribute any solicited AR data, ie, have at least one post-baseline solicited safety (eDiary) assessment. The Solicited Safety Set will be used for the analyses of solicited ARs and participants will be included in the vaccination group corresponding to the study vaccination they actually received.

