The number and percentage of subjects who reported any solicited AR, any solicited local AR, and any systemic solicited AR during the 7-day follow-up period after each vaccination will be tabulated by CMV serostatus, vaccination group, and vaccination, with a two-sided 95% exact CI using the Clopper-Pearson method.

The number and percentage of subjects who reported each individual solicited local AR (has a severity grade of Grade 1 or greater) and solicited systemic AR (has a severity grade of Grade 1 or greater) during the 7-day follow-up period after each vaccination will be tabulated by CMV serostatus, vaccination group, severity grade and vaccination.

The number and percentage of subjects who reported each individual solicited AR will also be summarized by CMV serostatus, vaccination group, severity grade, day of reporting and vaccination. The number and percentage of subjects experiencing fever (a temperature greater than or equal to 38.0°C/100.4°F by the oral, axillary, or tympanic route) by severity grade and the number and percentage of subjects experiencing a fever of Grade 3 or higher temperature (a temperature greater than or equal to 39.0°C/102.1°F by the oral, axillary, or tympanic route) in cumulative half-degree (°F) increments will be provided.

The onset of individual solicited AR is defined as the time point after each vaccination at which the respective solicited AR first occurred. The number and percentage of subjects with onset of individual solicited AR will be summarized by CMV serostatus, vaccination group, study day relative to corresponding vaccination (Day 1 through Day 7) and vaccination.

The duration (days) of each solicited AR will be summarized by CMV serostatus, vaccination group and vaccination. Duration will be calculated as the end day/date of the solicited AR event – the start day/date of the solicited AR event + 1, regardless of whether it is intermittent or continued. If the solicited AR continues beyond 7 days, the consecutive days a solicited AR is reported after 7 days will be included (eg, an event that lasted 5 days in the first 7 days post vaccination and 3 consecutive days beyond 7 days post vaccination, the duration will be reported as 8 (5+3) days.).

All solicited ARs (including rash) that continue beyond 7 days post vaccination will be presented in separate data listings.

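### SAP 5.2 gives a participant who received more than one product a single highest-dose label, so the per-vaccination solicited AR tables count some diaries under a higher dose than was injected at that vaccination

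*SAP*

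**What the plan says.** SAP 5.2 opens by placing participants according to the vaccine they received, as Protocol 9.4.2 does: "participants will be included in the vaccination group corresponding to the study vaccination they actually received". It adds that "a subset of the Solicited Safety Set is defined for each vaccination", which creates a First, a Second and a Third Vaccination Solicited Safety Set. Those definitions settle who is in each set. They do not say which group the person is counted in at that vaccination.

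The group is settled once, by a rule for misdosed participants. "Subjects who receive a vaccination/injection that is different from the vaccination/injection which the subject is randomized to" is the trigger, and the consequence is that they "will be summarized under the highest dose of vaccination group". A ranking of the three dose levels follows, with placebo last. SAP 5.3 repeats the rule for the Safety Set.

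SAP 6.3.2 states that counts of participants with solicited ARs "during the 7-day follow-up period after each vaccination will be tabulated by CMV serostatus, vaccination group, and vaccination". It also plans severity, day-of-reporting, onset and duration summaries for each vaccination. On precedence, the SAP Introduction says: "If the methods in this SAP differ from the methods described in the protocol, the SAP will prevail".

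**The concern.** The per-vaccination tables describe what happened in the seven days after a particular injection. The label attached to that injection should be what was in the syringe. A participant-level highest-dose label breaks that link for anyone who received two different products. A placebo participant given vaccine once, at the third visit, would have the saline diaries from the first two visits reported as vaccine experience. A vaccine participant given placebo once would have that saline diary reported at the vaccine dose.

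The relabelling runs only upward: the injection actually given is always the lower one. It therefore does not average out over participants. If reaction rates do not fall with dose, the expected result is a lower apparent rate in the higher-dose column and a flatter dose pattern. Solicited ARs after each vaccination are a primary endpoint (SAP 3.1).

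**Working it through.** The plan states no figure for this rule, so there is none to reproduce. The check has two parts: how many tables are mislabelled per participant, and how far one participant can move a rate.

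**1. Tables mislabelled**, taking the label as the highest dose received and three vaccinations given:

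| Randomized to | Received in error | Label | Tables with a label not matching the injection |
|---|---|---|---|
| Placebo | one active dose | that active dose | 2 of 3 |
| Low | one middle dose | middle | 2 of 3 |
| High | one placebo | high (unchanged) | 1 of 3 |
| Low | one placebo | low (unchanged) | 1 of 3 |
| Low | middle at every vaccination | middle | 0 of 3 |

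If each per-vaccination table uses the product given at that vaccination, the count is 0 in every row.

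**2. Cell sizes.** Protocol 4.1 gives, for each dose level in the Part 1 seropositive group, "Approximately 24 participants randomized 3:1 to receive either" vaccine or placebo: 24 × 3/4 = 18 vaccinees. The Part 1 seronegative group has 60 × 3/4 = 45. Part 2 adds 80 × 3/4 = 60 seronegative and 120 × 3/4 = 90 seropositive vaccinees at the selected dose. SAP 6.5 combines the Parts in the final analysis, so the selected-dose cells are 45 + 60 = 105 and 18 + 90 = 108. The two unselected levels stay at 45 and 18.

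**3. Largest shift from one participant.**

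- *Moved in* (a non-reacting lower-dose or placebo diary added to a cell of n): the rate goes from x/n to x/(n+1). The drop is x/[n(n+1)], at most 1/(n+1), reached when x = n.
- *Kept in* (a participant in a cell of n was given placebo or a lower dose at that visit and did not react): the rate should be x/(n−1) and is reported as x/n. The drop is x/[n(n−1)], at most 1/n, reached when x = n−1.

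| n | Moved in, 1/(n+1) | Kept in, 1/n |
|---|---|---|
| 18 | 1/19 = 5.3 points | 1/18 = 5.6 points |
| 45 | 1/46 = 2.2 | 1/45 = 2.2 |
| 105 | 1/106 = 0.94 | 1/105 = 0.95 |
| 108 | 1/109 = 0.92 | 1/108 = 0.93 |

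**4. Illustration with assumed rates.** Adding one non-reacting placebo diary:

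- 16/18 = 88.9% becomes 16/19 = 84.2%, a drop of 4.7 points.
- 40/45 = 88.9% becomes 40/46 = 87.0%, a drop of 1.9 points.
- 97/108 = 89.8% becomes 97/109 = 89.0%, a drop of 0.8 points.

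For scale, the exact 95% interval for 16/18 runs from 65.3% to 98.6%, so one participant's shift is well inside the sampling uncertainty.

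**The case against.** Three stronger readings are tempting, and the documents do not support them.

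- *Every misdosed participant goes to the top dose in the trial.* The word 'received' is missing from the rule, so a reader might infer this. But the sentence before it assigns by product received, and a ranking that ends in placebo makes sense only for choosing among products a person received. A high-dose participant given placebo once is therefore not moved, and someone given the same wrong product throughout is labelled correctly.
- *The SAP contradicts the protocol.* Protocol 9.4.2 assigns each participant by what was received and is silent on mixed exposure. The SAP fills that gap.
- *The rule affects dose selection.* SAP 6.5 records that the dose was chosen from the interim analysis with the 26 May 2020 cutoff. SAP version 5.0 governs the final analysis, and nothing shows that misdosing touched the interim.

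The best case on the merits is that per-vaccination assignment has its own oddities. A placebo participant first given vaccine at dose 3 would sit in the third-vaccination vaccine column beside people with two earlier doses, and someone given vaccine at dose 1 in error would later appear under placebo. The first oddity exists under the SAP rule too, so it does not favour that rule. The second matters little for a 7-day diary when planned injections are 55 and 112 days apart. It has real force for unsolicited AEs, where crediting events in a vaccine-exposed person to placebo is debatable, and there the participant-level rule is defensible.

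It also stands that frequency is unknown. Protocol 7.1 lists dosing error only as a reason for stopping vaccination. Someone stopped after a single wrong first dose has no mislabelled table. Misdosing will be visible in the administration listing (SAP 6.2.5) and, where classed as a major deviation, in the deviation outputs (SAP 6.2.6), although these do not correct the AR tables.

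**Conclusion.** The point holds as a minor defect confined to the per-vaccination solicited AR tables in the final analysis and CSR. Any participant with mixed exposure has at least one diary counted under a higher dose than was injected. One such participant shifts a rate by at most 5.3 to 5.6 points in an 18-person cell, 2.2 in a 45-person cell and about 0.9 in the pooled selected-dose cells. The unselected dose levels, which keep the small cells, are the most exposed.

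This rests on four assumptions: the label means highest dose received; planned enrolment is met (a larger Part 2 would make the pooled effect smaller); the maxima are worst cases with everyone else in the cell reacting; and the downward direction requires that reactions do not become less frequent with dose. A single placebo diary that does report a reaction could move a rate slightly the other way. With no mixed exposure the effect is nil. The study tests no hypothesis, so no formal decision turns on it.

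**What to change.** In SAP 5.2, state that group assignment in the First, Second and Third Vaccination Solicited Safety Sets follows the product and dose level actually received at that vaccination. For tables spanning all vaccinations, and for the Safety Set in SAP 5.3 including the unsolicited AE tables, keep the participant-level rule but word it as the highest dose actually received. Footnote misdosed participants in the affected tables.

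The cost is a few words of SAP text and one treatment variable per vaccination in the analysis datasets. The small downside is that a misdosed participant may appear in different columns across the three per-vaccination solicited AR tables, which the footnote explains. SAP version 5.0 is dated by its own account before the final database lock, so the wording can be settled before unblinded final tables are produced.
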